Unfortunately, following a low-potassium diet involves limiting or avoiding many plant-based sources of potassium, including nuts, seeds, legumes, and high-potassium fruits and vegetables. With accompanying dietary restriction requirements for sodium, phosphate and protein, the diet can be burdensome and unpalatable for the patients, and can make it difficult to obtain essential nutrients⁴. In addition to providing potassium, high-potassium plant foods are important sources of dietary fiber, organic anions (potential base), antioxidants and other phytochemicals (e.g., phytosterols), and therefore, a low-potassium diet may contribute to hypertension (low potassium), constipation and diarrhea (low fiber), dysglycemia and dyslipidemia (low fiber and other phytochemicals), metabolic acidosis (low organic anions), oxidative stress and inflammation (low antioxidants and other phytochemicals)⁴.

Patiomer is approved by the U.S. Food and Drug Administration (FDA) for the treatment of hyperkalemia, and has been demonstrated to be effective in treating hyperkalemia in CKD patients⁵. However, the potential of this new therapy for allowing CKD patients to liberalize their diets, and the potential health benefits of following a plant-rich diet in advanced CKD are yet unexplored.

4) **Inclusion and Exclusion Criteria**

The focus of the study is to: a) evaluate the efficacy of patiomer for managing serum potassium concentrations in CKD patients as they are transitioned to a plant-rich diet that includes high-potassium fruits and vegetables, and b) evaluate the impact of a plant-rich diet on health outcomes in CKD patients. We will recruit 10 CKD patients with persistently elevated serum potassium concentrations in New York City.

i. Inclusion criteria. In order to be eligible for the study, the individual must meet the following criteria:

a) 19-80 years of age

b) Stages 3-4 CKD (estimated glomerular filtration rate (eGFR) of 15-59 mL/min/1.73m², not

treated with dialysis)

c) No prior treatment with patiromer

d) Mild hyperkalemia (potassium 5.1 to <6.5 mEq/L) on one of the last two blood tests

e) No prior episodes of moderate-severe hyperkalemia (potassium \geq 6.5 mEq/L) in the past 6 months

f) Deemed appropriate for the intervention by the patient’s nephrologist, considering the patient’s prognosis, cognition and pending treatments (e.g., dialysis)

ii. Exclusion criteria. We will exclude from participation patients with the following characteristics:

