a) Change in medications that alter potassium homeostasis (e.g., RAAS inhibitors, diuretics, β -blockers) in the last month

b) Diagnosed with bowel diseases or syndromes (e.g., bowel obstruction, major GI surgery, short-bowel syndrome, irritable bowel syndrome, inflammatory bowel disease, chronic diarrhea)

c) Dietary restrictions (e.g., allergies) or otherwise unable/unwilling to adhere to study diets (excludes dietary restrictions on high-potassium foods)

d) Pregnant (females) or planning to become pregnant (males and females) during the study

If at any point during the study (including baseline) a participant has moderate-severe hyperkalemia (potassium \geq 6.5mEq/L), or if a participant becomes pregnant during the study, they will be withdrawn from the study.

Inclusion of women and minorities

Given the pilot nature of the intervention and small sample size (n=10), the study population will not be representative of the CKD population, and will have insufficient power to detect differences in intervention effects by sex and race/ethnicity. To our knowledge, plant-rich diets, such as those being investigated in this study, have similar health effects by sex and race/ethnicity. No individual will be excluded from the study on the basis of sex or race/ethnicity alone, and we will attempt to obtain a sample that reflects the demographics of our source population.

5) Study-Wide Number of Subjects

We will recruit a total of 10 individuals to the study. We have secured the support of the New York Harbor VA Healthcare System, which served approximately 250 non-dialysis CKD patients in the New York City area, as well as the Division of Nephrology at NYU Langone Health. It is estimated that approximately 10% of these patients have hyperkalemia. Thus, we have no concerns about our ability to access and recruit the required number of participants for this study. The estimate demographic breakdown of patients at the renal clinic are 95% male with 40% white, 25% black, 20% Hispanic, 10% Asian, and 5% other racial/ethnic background. The planned enrollment is outlined in Table 1.

Table 1. Planned enrollment report

Racial Categories	Ethnic Categories				Total
	Not Hispanic or Latino		Hispanic or Latino		
	Female	Male	Female	Male	
American Indian/ Alaskan Native	0	0	0	0	0
Asian	0	1	0	0	1
Native Hawaiian or Other Pacific Islander	0	0	0	0	0
Black or African American	0	2	0	1	3
White	1	3	0	1	5

More than 1 race	0	1	0	0	1
Total	1	7	0	2	10

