6) Study-Wide Recruitment Methods

Potential participants will be identified using two recruitment methods: 1. Referral by the patient's nephrologist, and 2. DataCore directed search of electronic medical records. Nephrologist referral patients will be obtained from the New York Harbor VA Healthcare System, NYU Langone Health, and Bellevue Hospital. The DataCore directed search of electronic medical records will be limited to patients of nephrologists in the Division of Nephrology who have an episode of mild hyperkalemia in the past 6-months. Once identified using the electronic medical record search, the patient's nephrologists will be notified about their potential eligibility. Per the study inclusion criteria, nephrologists will be asked to confirm that the patient is appropriate for the study.

- (a) [name] or [name] will review each section of the written consent form with the referred participant, ask the participant if they understand each section, and clarify any questions they may have. The participant and the person obtaining consent will sign and date the consent form. Copies of the consent, which includes the contact information of the PI ([name]), will be provided to the participant and sent to the patient's nephrologist. Informed consent will be considered an ongoing process throughout the study, and participants' questions regarding their rights and responsibilities will be addressed whenever they occur.
- (b) Once enrolled, [name] and [name] will meet to verify that the participant meets the inclusion/exclusion criteria. This information will be obtained from the patient's electronic medical record.
- (c) Study staff will contact eligible patients, and schedule a fasting screening appointment (at least 8 hours of fasting).

A fasting blood sample will be obtained at the screening visit, and analyzed for potassium. If this test is in the range of mild hyperkalemia (potassium 5.1 to <6.5 mEq/L), the participant will be deemed to have persistent hyperkalemia, and be accrued. Otherwise they will be deemed ineligible, and excluded from the study. Regardless of enrollment status, all eligible patients who are invited to participate in the study will be reimbursed \$25.00 for time and travel expenses incurred by attending the screening visit.

7) Study Timelines

We will recruit 10 participants. Given the intensiveness of the intervention, no more than two participants will be enrolled in the intervention at a time.

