8) Study endpoints

Among 10 stages 3-4 CKD patients with persistent, mild hyperkalemia, we will evaluate, in a quasi-experimental, controlled feeding study, the efficacy of patiomer for maintaining normal serum potassium concentrations when following a plant-rich diet that includes high-potassium fruits and vegetables, as well as the effects of this diet on health outcomes. The participants will be transitioned gradually to a plant-rich diet, as outlined further below.

The interventions will be evaluated primarily in terms of serum potassium concentrations, but health outcomes will also be assessed, including blood pressure, gastrointestinal symptoms, and fasting concentrations of phosphorus, calcium, magnesium, albumin, glucose, insulin, cholesterol, LDL-cholesterol, HDL-cholesterol, triglycerides, urea nitrogen, bicarbonate and C-reactive protein. For all parameters, baseline values will be compared to values at the end of each diet phase (weeks 2 and 4).

9) **Procedures involved**

a. Design.

We will conduct an unblinded, quasi-experimental, controlled feeding study, which will be coordinated through the New York University – Health and Hospitals Corporation Clinical and Translational Science Institute (CTSI). Throughout the study, participants will be prescribed patiromer by the study nephrologist ([name]), which will be administered through the CTSI pharmacy. After a 1-week stabilization period, in which participants are prescribed Patiromer while following their usual diets, the feeding component of the study will occur in two phases. During the first phase (week 2), participants will be transitioned to a plant-rich renal diet, which contains moderate protein (10-15% of kcal), restricts dairy products (≤ 1 serving/day), and eliminates high-potassium fruits and vegetables. During the second phase (weeks 3 and 4), the diet will be altered to provide at-least half of fruits and vegetables from high-potassium sources. To reduce participant burden, meals will be delivered to participants by Portable Chef (New York, NY) three times per week.

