iii. Serum potassium concentrations. The primary purpose of this study is to evaluate the efficacy of patiromer for maintaining serum potassium concentrations in CKD patients during transition to a liberalized plant-rich diet by comparing fasting serum potassium concentrations at screening to values at the end of phase I (week 2) and phase II (week 4) of the study. However, because potassium concentrations are also being used to titrate the dose of patiromer needed to achieve normal potassium concentrations, fasting serum potassium concentrations will also be measured at the end of weeks 1 and 3. To ensure a rapid response to changes in serum potassium concentrations, blood samples obtained at the CTSI CRC will be immediately delivered to the study laboratory at Tisch Hospital for analysis, and the results sent to the CTSI Pharmacy for evaluation (section 10.a.i.). Participants will be directed to pick up new prescriptions from the CTSI Pharmacy on the days of measurement. To obtain a measurement of serum potassium concentration, a 0.5 mL sample of blood is required.

iv. Blood pressure. Systolic and diastolic blood pressures will be measured after 5-minutes of rest in a seated position with their arm supported at the level of their heart and their feet resting on the floor using an automatic sphygmomanometer. Blood pressure measurements will be obtained in duplicate with a third measure obtained if the systolic or diastolic values on repeated measurement differ by more than 5 mmHg.

v. Gastrointestinal symptoms. The frequency and severity of participant gastrointestinal symptoms in the previous week (abdominal cramping, abdominal discomfort, indigestion, infrequent or difficult to pass bowel movements, flatulence, loose or watery stools) will be self-reported via an investigator-developed questionnaire at baseline, and at the end of the stabilization period (week 1), phase I diet (week 2), and phase II diet (week 4).

vi. Other biochemical parameters. Fasting blood samples will be obtained at the CTSI CRC, and analyzed for concentrations of phosphorus, calcium, magnesium, albumin, glucose, insulin, cholesterol, LDL-cholesterol, HDL-cholesterol, triglycerides, urea nitrogen, bicarbonate and C-reactive protein. Similar to serum potassium concentrations, blood samples will be delivered by study staff to the laboratory at Tisch Hospital for analysis. To obtain these biochemical measurements, approximately 5.0 mL of blood is required.

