Table 4. Summary of study visits and procedures

	Screening	Baseline	Wk 1	Wk 2	Wk 3	Wk 4
Baseline Questionnaire (comorbidities, sociodemographics, tobacco and alcohol use, use of dietary supplements and urine output)		X				
Medical Chart Review (cause of CKD, comorbidities, urine albumin concentration)		X				
Medical Chart Review (medications)		X		X		X
Dietary Assessment (3-day food record)			X			
Anthropometrics (height)	X					
Anthropometrics (weight)	X			X		X
Fasting Blood Test (potassium)	X		X	X	X	X
Fasting Blood Test (phosphorus, calcium, magnesium, albumin, glucose, insulin, cholesterol, LDL-cholesterol, HDL-cholesterol, triglycerides, urea nitrogen, bicarbonate and C-reactive protein)		X		X		X
Blood Pressure (systolic and diastolic blood pressure)		X		X		X
Gastrointestinal Symptoms Questionnaire (frequency and severity of abdominal cramping, abdominal discomfort, indigestion, infrequent or difficult to pass bowel movements, flatulence, loose or watery stools in previous week)		X	X	X		X

10) Data and Specimen Banking

No samples will be stored for future analyses in this study.

11) Data Management

Information to be obtained from participants includes height and weight, blood pressure, medical history, blood tests, and self-administered questionnaires (sociodemographics, clinical and comorbid conditions/ management, cigarette and alcohol use and gastrointestinal symptoms). None of the data to be collected is considered sensitive in nature. Some of the participant data such as laboratory results will be linked to the participant's name. Other data (e.g., height, weight, blood pressure, medical history, and surveys) will be linked to the participant through a subject ID number. As a further measure to protect participants' privacy, different subject ID numbers will be used for study measurements and for coordinating the feeding component of the study. We will maintain separate files for identified and de-identified data in locked file cabinets in a locked office. Access to these data will be restricted to the PI ([name]), and study staff responsible for gathering data and maintaining research files. Data will be entered into a centralized database maintained on a secure server. Data

in these files will be linked to participants only through their ID number – this file will be maintained in a locked filing cabinet at [name]. All data collected will be used expressly for the purpose of the proposed study.

a. Overview.

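### The primary potassium change starts from the screening value that decides entry, so in a one-group study regression to the mean is counted as effect

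*Combined protocol and SAP*

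**What the plan says.** - **Reference value.** Section 9.b.iii serves the study's primary purpose by "comparing fasting serum potassium concentrations at screening to values at the end of phase I (week 2) and phase II (week 4".
- **Entry rule on the same sample.** Section 6: "If this test is in the range of mild hyperkalemia (potassium 5.1 to <6.5 mEq/L), the participant will be deemed to have persistent hyperkalemia". Anyone outside that range is excluded.
- **Earlier filter.** Section 4 requires "Mild hyperkalemia (potassium 5.1 to <6.5 mEq/L) on one of the last two blood tests", with no value of 6.5 or more in the past 6 months. Under section 6(b), two team members "will meet to verify that the participant meets the inclusion/exclusion criteria" from the medical record.
- **No untreated comparison.** Section 9.a describes one unblinded group: "After a 1-week stabilization period, in which participants are prescribed Patiromer while following their usual diets". The week 1 potassium is therefore already on treatment.
- **Schedule.** The Table 4 row "Fasting Blood Test (potassium)" is marked at Screening and Weeks 1 to 4. Its Baseline cell is blank, although the other fasting chemistry is drawn at that visit. Section 10 adds: "No samples will be stored for future analyses in this study".
- **Analysis.** Sections 8 and 11.a compare *baseline* with the end of each diet phase. Section 11.a uses repeated-measures ANOVA with Tukey HSD and summarises the proportion with hyperkalemia at each time point. Regression to the mean is not mentioned.

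**The concern.** A single potassium reading is the person's usual level plus a temporary deviation. Admitting only people whose screening reading is at least 5.1 selects for upward deviations, which fade by weeks 2 and 4 whatever is given. Using that reading as the starting point puts the fading into the estimated change.

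The chart filter weakens this, because it favours people whose usual level is high. It cannot remove it, because only one of two earlier tests need be raised and the screening value is still selected.

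The same applies to the descriptive proportion with hyperkalemia. It is 100% at screening by construction, so it can hardly do anything but fall. The measured week 2 and week 4 levels are valid as levels. Crediting normal levels to patiromer, which is the hypothesis in section 2, is less secure, because some untreated people would also read below 5.1. Section 2 says success would lead to a randomized trial, so the estimate and its attribution matter.

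**Working it through.** **Inputs from the protocol.** Screening window 5.1 to <6.5; one of the last two chart values in that window and none at 6.5 or above; n = 10; screening, week 2 and week 4 compared by repeated-measures ANOVA and Tukey HSD. For the source clinic, section 5 says: "It is estimated that approximately 10% of these patients have hyperkalemia".

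**Not in the protocol.** Potassium mean, SD, test-retest correlation and alpha. There is no planned figure to reproduce, so everything below is an illustration under a true change of zero, normal values and alpha 0.05.

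**Step 1: screening rule alone, closed form.** Let σ be the SD of a single reading, ρ the test-retest correlation, and p = 0.10 the share of readings at or above 5.1. Ignoring the upper limit,

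expected fall = (1 − ρ) × σ × φ(z) / p, with z = 1.2816 and φ(z) = 0.1755.

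For σ = 0.5 and ρ = 0.6, the population mean is 5.1 − 1.2816 × 0.5 = 4.46, and the fall is 0.4 × 0.5 × 0.1755 / 0.10 = 0.351 mEq/L.

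**Step 2: add the chart filter.** Simulating the whole entry path with the same σ and ρ gives 0.256. The filter removes (0.351 − 0.256) / 0.351 = 27% of the fall and leaves the rest. Over σ 0.4-0.6 and ρ 0.5-0.8, the fall is 0.10-0.40.

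**Step 3: wider grid, full entry rule.** Between-person SD 0.3-0.4, within-person SD 0.2-0.4, independent within-person deviations. The Tukey column uses n = 10, between-person SD 0.35 and three time points. It counts trials that wrongly separate screening from week 2 or week 4.

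| Source population | Fall, screening to untreated retest (mEq/L) | Retest below 5.1 | Mean of two chart values minus retest | False Tukey difference |
|---|---|---|---|---|
| Mean 4.8-5.2 | 0.04-0.32 | 13-49% | 0.01-0.11 | 6-37% |
| 10% have a usual level ≥5.1 (means 4.59-4.72) | 0.10-0.36 | 30-53% | 0.03-0.13 | 21-49% |
| 10% have a single test ≥5.1 (means 4.38-4.64) | 0.11-0.45 | 32-65% | 0.04-0.18 | 24-68% |

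The first row implies that 20-61% of single readings are at or above 5.1, which is more than section 5's 10%. Referral may enrich the pool, so the truth may lie between the rows. With a fresh, unselected baseline the false Tukey rate is about 4%. If all five potassium time points enter the Tukey test, the first row's rate becomes 2-20%, against 1.2-1.3% with a fresh baseline.

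**Step 4: deviations that persist.** Assume weekly autocorrelation 0.3-0.7, mean 5.0, SDs 0.35 and 0.3, and chart tests 8 and 16 weeks before screening. The spurious fall from screening is then 0.10-0.15. Measured from a new baseline it is 0.04-0.08 if that draw is one week after screening, 0.01-0.06 at two weeks and 0.003-0.04 at three weeks. A new baseline is better, but not perfect when the gap is short.

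**The case against.** **A separate baseline potassium may be intended.** Section 4 withdraws anyone at 6.5 or above at any time, baseline included. Such a person would already have failed screening, so the wording fits a later draw. Section 9.b also says measures are taken at baseline unless noted otherwise. This stands as an inconsistency. The natural reading is still that baseline potassium means screening: Table 4 schedules no such draw, and section 9.b.iii names screening as the reference.

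**Other potassium values exist.** Section 12 provides a confirmatory test for abnormally high or fast-rising results, but it is conditional and not a reference. Chart values are partly selected, may be non-fasting or from another laboratory, and are not in section 9.b's list of chart data to collect. They support only a rough sensitivity analysis.

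**The aim is maintenance, and patiromer's effect is taken as known.** Tukey also compares week 2 with week 4, where neither value decided entry, so the question about adding high-potassium foods is largely untouched. That stands. The comparison named as primary is nonetheless with screening. The fall in the proportion with hyperkalemia is a separate descriptive summary and is not itself tested.

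**The size is assumed.** True: the range runs from trivial to important. The direction does not depend on the assumptions.

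**It is a disclosed one-group proof of concept.** Also true. No success threshold rests on this change, which limits the harm.

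**Conclusion.** The concern holds. Followed as written, the plan counts regression to the mean in its primary comparison and has no means of subtracting it. The mechanism follows directly from sections 6, 9.a, 9.b.iii and Table 4.

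The size is illustrative because it rests on assumed means, SDs and normality. A fall of 0.04-0.45 mEq/L with no true effect covers all the settings tried, or 0.10-0.45 if the clinic's 10% is taken at face value. The false-positive rates also assume independent within-person deviations.

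The consequence is a biased estimate and over-attribution to patiromer, not a wrong formal decision. It should be fixed, and the fix is cheap.

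**What to change.** **Preferred.** In Table 4, add potassium to the fasting sample at Baseline, before the first patiromer dose. Name that value as the reference in sections 8, 9.b.iii and 11.a. Keep screening for eligibility only, and do not re-select participants on the new value; section 4's withdrawal rule is left as it stands. State the screening-to-baseline interval, since a short one leaves some bias.

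**Cost.** Ten potassium assays at a visit that already draws fasting blood. Section 9.b lists 0.5 mL for potassium and about 5.0 mL for the other assays, so at most 5.0 + 0.5 = 5.5 mL if they cannot share a sample. The reported fall will probably be smaller. Some participants will read below 5.1 at the new baseline (13-65% in the scenarios above, fewer if deviations persist and the gap is short). The sponsor must therefore settle beforehand which value *baseline* means in the section 4 withdrawal text and the section 9.a.i dosing text, and reconcile both with Table 4.

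**If no draw is added.**
- Report the change from screening, and the fall from 100% with hyperkalemia, as including regression to the mean.
- Apply the same caveat when attributing week 2 and week 4 levels to patiromer.
- Add the last two chart potassium values to section 9.b's chart data, and show the change from their mean as a sensitivity analysis. That reference still overstates the untreated level, by 0.01-0.18 mEq/L in the scenarios above.
- Use week 1 as a reference only for the diet-transition question, since it leaves out patiromer's initial effect.

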Another intervention feature to lower the risk of hyperkalemia is the close monitoring of participants’ serum potassium concentrations to adjust the dose of patiomer (10.a.i. Table 2). We will measure serum potassium concentrations as per current patiomer recommendations (weekly), and samples will be processed through the Tisch Laboratory, and the results sent to the CTSI Pharmacy for review. If values are abnormally high or rapidly increasing towards hyperkalemia (10.a.i. Table 2), the study nephrologist ([name]) will be immediately contacted. Because hemolysis can cause artificially elevated serum potassium values, participants with abnormally high or rapidly increasing concentrations of serum potassium will have another blood test to confirm their serum potassium concentrations.

In addition to risks associated with hyperkalemia, there are potential risks related with patiromer use. In a sample of 734 patients treated with patiromer, the most common AEs were constipation (7.2%), hypomagnesemia (5.3%), diarrhea (4.8%), nausea (4.8%), abdominal discomfort (2.0%) and flatulence (2.0%). It is likely that the most common of these AEs (constipation, hypomagnesemia, diarrhea) would be attenuated by a plant-rich diet, which contains higher amounts of fiber and magnesium compared to the typical Western diet. The less common adverse events (abdominal discomfort, flatulence) may be exacerbated by the higher intakes of dietary fiber. These potential AEs will be assessed at the end of each week through the gastrointestinal symptoms questionnaire, and blood testing at the end of phase I and II (for hypomagnesemia). Patiromer also has the potential to bind to other medication, reducing their absorption. This will be mitigated by directing patients to take patiromer once daily, and at least 3 hours away from other medications.

It is unlikely that women and men with stages 3-4 CKD will become pregnant or impregnate someone. Additionally, we will exclude anyone who is planning on becoming pregnant from the study. As part of our Clinical Trial Agreement with Relypsa, Inc., we will report any pregnancies (whether female or male impregnating a female) to Relypsa, Inc. In addition, because the patiromer and the research diets are untested in pregnant women, we will withdraw women who become pregnant during the study period.

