A brief description of the study will be provided at the time of screening for the study. After reviewing the consent form with patients, and after they have signed the consent form, we will verify that they meet the inclusion/exclusion criteria (sections 5.i and 5.ii.). Potential participants will be shown the research diet menus to determine whether they are willing and able to adhere to the research diets. All questions will be answered.

A copy of the consent form will be given to the participant and they will be encouraged to contact the PIs with any and all questions that occur at any time during the conduct of the study. No patients will be excluded on the basis of race/ethnicity, but this pilot study has a sample size that is insufficient to examine differences in the intervention by race/ethnicity.

30) Process to document consent in writing

Patient's consented participation in this study will be documented in their medical record.

31) Drugs or devices

Participants in this study will be prescribed patiromer (dosing 10.a.i. Table 2), under the supervision of the study nephrologist ([name]). Patiromer is an FDA-approved cation-exchange polymer that binds to potassium in the digestive tract, and is excreted (along with bound potassium) in feces. Patiromer is indicated for the treatment of hyperkalemia, and is demonstrated to result in clinically significant reductions in serum potassium concentrations. The safety concerns associated with patiromer, along with measures to reduce these complications, are noted in section 13, and include constipation (7.2%), hypomagnesemia (5.3%), diarrhea (4.8%), nausea (4.8%), abdominal discomfort (2.0%) and flatulence (2.0%), and binding to other medications.

References.

1. United States Renal Data System. 2016 USRDS annual data report: Epidemiology of kidney disease in the United States. National Institutes of Health, National Institute of Diabetes and Digestive and Kidney Diseases, Bethesda, MD, 2016.
4. St-Jules DE, [name] DS, Sevick MA. Nutrient non-equivalence: Does restricting high-potassium plant foods help to prevent hyperkalemia in hemodialysis patients? *J Ren Nutr* 2016;26(5):282-287.

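### Nausea is the only adverse event listed for patiromer with no prompted assessment described: the GI questionnaire has no nausea item

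*Combined protocol and SAP*

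**What the plan says.** Section 12, in its account of the risks of patiromer, gives adverse event rates from 734 treated patients: constipation 7.2%, hypomagnesemia 5.3%, diarrhea 4.8%, nausea 4.8%, abdominal discomfort 2.0% and flatulence 2.0%. Two sentences follow on which events a plant-rich diet might ease or worsen. The section then commits to an assessment: "These potential AEs will be assessed at the end of each week through the gastrointestinal symptoms questionnaire, and blood testing", where the blood testing is for hypomagnesemia at the end of phases I and II.

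Section 9.b.v describes the instrument as an investigator-developed, self-reported questionnaire on the frequency and severity of symptoms in the previous week, namely "abdominal cramping, abdominal discomfort, indigestion, infrequent or difficult to pass bowel movements, flatulence, loose or watery stools". It is given at baseline and at the end of weeks 1, 2 and 4. Table 4 repeats the content ("frequency and severity of abdominal cramping, abdominal discomfort, indigestion, infrequent or difficult to pass bowel movements, flatulence, loose or watery stools in previous week") and marks the same four time points.

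Section 31 names nausea again among the safety concerns: "diarrhea (4.8%), nausea (4.8%), abdominal discomfort (2.0%) and flatulence (2.0%), and binding to other medications".

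Section 12 also commits the principal investigator to report all adverse events from consent until 14 days after the intervention.

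**The concern.** The safety section appears to promise that the questionnaire will pick up the listed gastrointestinal events, yet one of them is not on the form as described. That event is as frequent as diarrhea in the protocol's own figures and more than twice as frequent as abdominal discomfort or flatulence, all of which are asked about.

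What is at stake is comparability within the tolerability data. The symptoms on the form are prompted, graded for frequency and severity, and measured before treatment. Nausea would come in only by whatever route general adverse event reporting provides. It would therefore probably be under-counted relative to the others. With no control arm, the baseline value is the only comparator in this study, and nausea would have none. It also could not enter the Section 11 analysis of change in gastrointestinal symptoms between baseline and the end of each diet phase.

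**Working it through.** The plan gives no figure for this point, so the check is a comparison of the lists, followed by one calculation for scale.

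**Step 1. Match each event listed in Section 12 to a planned assessment.**

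| Event (rate, Section 12) | Item in 9.b.v and Table 4 | Other scheduled measure |
|---|---|---|
| Constipation (7.2%) | Yes, the bowel movement item | – |
| Hypomagnesemia (5.3%) | No | Magnesium blood test |
| Diarrhea (4.8%) | Yes, the loose stools item | – |
| Nausea (4.8%) | No | None |
| Abdominal discomfort (2.0%) | Yes | – |
| Flatulence (2.0%) | Yes | – |

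Four of six events have a questionnaire item, one has a blood test, and one, nausea, has neither. The two remaining questionnaire items, cramping and indigestion, do not correspond to any listed event. Both descriptions of the form name the same six symptoms, and neither presents them as examples.

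**Step 2. Look for another prompt.** No other row of Table 4 asks about symptoms during treatment. The adverse event text in Section 12 sets a duty to report and gives deadlines. It does not say how events are to be elicited at visits.

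**Step 3. Compare the timing.** Section 12 has the questionnaire completed weekly. Section 9.b.v and Table 4 have it at baseline and weeks 1, 2 and 4, with nothing at week 3. Each questionnaire looks back one week, so symptoms confined to week 3, the first week on high-potassium fruits and vegetables, fall outside every recall window. This applies to every item on the form.

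**Step 4. Scale.** Inputs: rate 0.048 (Section 12) and n = 10 (Section 5).

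- Patients with nausea in the quoted sample: 0.048 × 734 = 35.2
- Expected cases among 10: 10 × 0.048 = 0.48
- Chance of no case: 0.952^10 = 0.611
- Chance of at least one case: 1 − 0.611 = 0.389

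Diarrhea has the same quoted rate, so its figures are identical. The calculation assumes that the rate carries over to these participants over 4 weeks. The documents give no rate for drug and diet together.

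**The case against.** Several points can fairly be made in the plan's defence.

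- **Section 12 may not mean nausea.** The two sentences just before the commitment name the other five events and skip nausea. If the commitment refers back only to those five, nothing is contradicted, because all five have an assessment. This reading is possible, so a flat contradiction cannot be claimed. It does not close the gap, since nausea would then have no stated assessment at all.
- **General reporting covers it.** A reader might infer that nausea will never be solicited or captured. The documents do not support that. Section 12 defines adverse events to include any unfavorable symptom and requires all of them to be reported, and participants attend visits in weeks 1 to 4. The protocol is silent on how events are elicited there. What stands is that no prompt for nausea is described.
- **The form itself is not shown.** The point rests on its described content. If the form already has a nausea item, the two descriptions need correcting instead.
- **Indigestion is close enough.** It is a neighbouring symptom, but the protocol lists nausea as a separate event and nowhere equates the two.
- **The main safety monitoring lies elsewhere.** This is correct. Section 12 names cardiotoxicity from hyperkalemia as the major risk, and monitoring rests chiefly on weekly potassium. No dosing, withdrawal or stopping rule uses the questionnaire.
- **The numbers are small.** Also correct. The same calculation gives a 61% chance of no case, and one or two cases in a study without a control arm could not be attributed to drug or diet.

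**Conclusion.** The point holds as a minor gap. Nausea is the only event in the protocol's own list for which no prompted assessment is described, whichever way the Section 12 sentence is read. As written, it would be collected less sensitively than the other gastrointestinal events and without a baseline. The consequence is confined to the tolerability data and the secondary gastrointestinal outcome.

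A reader might go further and infer that nausea, by causing missed doses or uneaten meals, would distort the potassium endpoint. The documents show no such effect. Diet deviations are recorded directly whatever their cause (Sections 9 and 12), and a nausea item would not measure missed doses.

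The probability of 0.39 illustrates scale under the assumption stated with the calculation; it does not measure harm. The finding on the missing item is firm as to the described content of the form. The mismatch over week 3 is a separate, plain inconsistency in the same Section 12 sentence.

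**What to change.** Add a nausea item, asking frequency and severity in the previous week like the others, to the questionnaire as described in Section 9.b.v and Table 4, from baseline onward.

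Reconcile the weekly schedule in Section 12 with the schedule in Section 9.b.v and Table 4. Either add the questionnaire at week 3, when participants already attend for a potassium test, or amend Section 12 to state the time points actually planned.

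Section 11 already analyses gastrointestinal symptoms as a group and needs no change.

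The cost is one extra line on a self-administered form that the study team developed itself, so no published scale is disturbed. The nausea item needs no added visit, blood sample or participant. Adding week 3 would mean one more completion of the form at an existing visit.
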